**Data validation:**

All variables used in the analysis will be checked for obvious outliers and inconsistencies.

**Data template:**

Based on this SAP, the statistical analyst will develop a tailored data template illustrating the data structure required for the statistical analyses.

#### 4. PROTOCOL DEVIATIONS WITH BEARING ON THIS STATISTICAL ANALYSIS PLAN

---

The following details in this SAP represent deviations from the protocol.

Header in the protocol	Change	Reason
(currently no deviations)		

[figure not shown]
#### 5. OUTLINE

---

The anticipated (predefined) outline of the manuscript is illustrated below.

**Figure 1. Flow diagram**

*Anticipated plot design, illustrating potential reasons for exclusion:*

**Table 1.** Characteristics of primary knee arthroplasty procedures.

Characteristics	Primary knee arthroplasties (n = )
Age, years	
Females, n (%)	
Implant type, n (%)	
- TKA	
- Medial UKA	
- Lateral UKA	
- Patellofemoral UKA	
- Unspecified UKA	
- Rotating hinge prosthesis	
- Rotating hinge prosthesis with condyle resection	
- Resection prosthesis	
- Partial resurfacing	
- Unspecified implant type (KNGB09, KNGB14, KNGB99)	
- Isolated patella	
Region for the procedure, n (%)	
- Northern Region of Denmark	
- Middle Region of Denmark	
- Southern Region of Denmark	
- Zealand Region of Denmark	
- Capital Region of Denmark	
- Private hospitals	
- Unknown	
Indication for the primary procedure, n (%)	
- Idiopathic knee osteoarthritis	
- Secondary knee osteoarthritis	
- Sequelae following tibia condyle fracture	
- Sequelae following femur condyle fracture	
- Sequelae following patella fracture	
- Rheumatoid arthritis	
- Sequelae following other arthritis	
- Haemophilia	
- Primary bone tumour	
- Metastatic bone tumour	
- Unknown	
Duration of the procedure, minutes	

Values are means (SD) unless otherwise stated.

Abbreviations: TKA = total knee arthroplasty. UKA = unicompartmental knee arthroplasty

*Further statistical information related to table 1:*

Data will be presented as mean with standard deviation (SD) when normally distributed or as median with interquartile range in case of skewed data. Dichotomous and categorical data will be presented in proportions. Normality of the data will be assessed using Q-Q plots, and histograms.

**Table 2.** Annual occurrence of primary procedures and major n-grade revisions.

Year	Primary procedures, n	1 st revision, n	2 nd revision, n	....	n grade revision, n	Maximal grade of revision performed*
1998						
1999						
2000						
2001						
2002						
2003						
2004						
2005						
2006						
2007						
2008						
2009						
2010						
2011						
2012						
2013						
2014						
2015						
2016						
2017						
2018						
2019						
2020						
2021						

Only grades of revisions with occurrences >10 are shown

\*The maximal grade of revision performed is defined as the single greatest grade of revision performed that year

**Table 3:** Annual occurrence of all n-grade revisions (including both major and minor revisions).

[figure not shown]
Year	1 st revision	2 nd revision	....	n grade revision	Maximal grade of revision performed*
1998					
1999					
2000					
2001					
2002					
2003					
2004					
2005					
2006					
2007					
2008					
2009					
2010					
2011					
2012					
2013					
2014					
2015					
2016					
2017					
2018					
2019					
2020					
2021					

Only grades of revisions with occurrences >10 for all years are shown

\*The maximal grade of revision performed is defined as the single greatest grade of revision performed that year

[figure not shown]
**Figure 2.** The standardized prevalence and incidence rates of n-grade revisions from 1998 to 2021.

*Anticipated plot design, illustrating with imaginary data, A-D*

Panel A and B illustrates standardized prevalence and incidence of major n-grade revisions. Panel C and D illustrate standardized prevalence and incidence of all n-grade revisions (including both major and minor revisions). Only grades of revisions with occurrences >10 are shown; for prevalence, >n-grade revisions are reported as well.

**Figure 3.** The standardized prevalence of patients with their total sum of revisions.

Panel A illustrates standardized prevalence of patients with major n-grade revisions. Panel B illustrates standardized prevalence rates of patients with all n-grade revisions (including major and minor revisions). The total sum of revisions is the summation of all revision procedures performed on a patient. E.g., a patient with 3 revisions performed on one knee and 4 revisions performed on the other knee, is categorized as a 7-grade revision patient. Only grades of revisions with occurrences >10 are shown as well as >n-grade grade revisions.

[figure not shown]

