Revision after knee arthroplasty is associated with significant financial costs for both the patient and society. For the patient, this is associated with a loss of ability to work, as described in the previous section. For Denmark's public health service, revision surgery is a significant financial burden. Revision surgery is more complex, requires longer operating time, more experienced surgeons, more advanced equipment and prostheses, and is usually performed in patients with comorbidities and who require more medication and a longer hospital stay (6, 45, 46). In addition, revision due to infection is more than 3 times as expensive as revision surgery for other reasons, which is a cause for concern as studies have found an increasing incidence rate of revisions due to infection (5, 12, 45-47). Gabor et al. conducted a prospective study in 2019 which suggested that centralizing revision surgery has the potential to limit costs (48).

Purpose

There is a need to prevent the complications that lead to repeated revisions, and there is a need to improve revision outcomes. Many unanswered questions are presented in the background section. Answers to these are needed in order to 1) predict the future need for

resources, 2) monitor the effects of changes in treatments and organization, and 3) give patients realistic expectations about the future when they undergo knee replacement surgery.

This research project aims to obtain new knowledge about the epidemiology of revisions after knee arthroplasty and to answer the following questions:

1. How many patients live with a multiple revision knee (i.e. prevalence) and how many multiple revisions procedures are performed (i.e. incidence)?
2. Are some demographic groups particularly at risk?
3. What is the risk of needing a revision after n-grade revision?
4. What future demands can be expected of surgeons and hospitals to provide care for patients needing revisions?
5. What is the lifetime risk of multiple revisions?

In order to answer the research questions, the research project is divided into 3 work packages.

WP-A1: Incidence and prevalence

The purpose of this work package (WP) is to determine the evolution of the incidence and prevalence of revisions of various degrees over the last two decades. We also aim to develop a mathematical model that predicts future incidence and prevalence based on demographic data as well as historical information of primary knee arthroplasty.

Research questions

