## 1. STUDY OVERVIEW

---

**Background and rationale** Knee arthroplasty is a common procedure performed worldwide to improve the quality of life for patients with degenerative knee conditions, trauma, and tumours. Complications can occur after knee arthroplasty, which may lead to a revision procedure, where at least one implant is exchanged, added, or removed. As the number of primary procedures in the world is increasing, so is the corresponding number of revisions. Some patients may require additional revision procedures, and some may end in a negative spiral of repeated revisions; We define three or more revisions on the same knee as being 'multiply revised'. The clinical impression of multiply revised patients is that the repeated occurrence of complications has significant impacts on the patients' quality of life including chronic pain, decreased independence, and increased morbidity. No study has yet investigated the incidence and prevalence of multiply revised knee arthroplasty patients stratified by previous revisions. To improve the care of multiply revised patients, epidemiological information is required which is the rationale of this study.

**Objectives** The aim of this observational study is to investigate the incidence and prevalence of multiply revised knee arthroplasty patients in all Danish patients with primary knee arthroplasty.

**Hypothesis** The number and burden of knee arthroplasty revision procedures and patients in Denmark has increased dramatically in the last 23 years.

**Methods** This is an observational study. Data will be collected from all primary and revision knee arthroplasties performed in Denmark from January 1st 1998 to 31st December 2021. Data will be acquired from two registers: The Danish Knee Arthroplasty Register (DKR), containing surgeon-reported data on primary and revision knee arthroplasties. In addition, data will be acquired from Landspatientregisteret, which contains all clinical data collected during any visit to a public or private healthcare facility in Denmark.

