### PICOTS

**Population:** All Danish citizens who have received a primary knee arthroplasty at a Danish healthcare facility, from the 1st of January 1998 to the 31st of December 2021

**Intervention/Exposure** Multiple revision knee arthroplasties in the same knee

**Comparator:** None

**Outcome (primary):** Annual standardized prevalence and incidence of n-grade revisions following knee arthroplasty between 1998 and 2021 in Denmark.

**Time:** Retrospectively, from the 1st of January 1998 to the 31st of December 2021, i.e., up to 24 years follow-up.

**Study design:** Observational retrospective register study.

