Calculation of standardized incidence: Annual standardized incidence is calculated as the number of new n-grade revisions performed as a proportion of the population in Denmark during a specific year. The population size of Denmark is defined as the population size at January 1st for that year (3). The incidence is then multiplied by 100,000 for standardization. This is done for each level of revision, each year. E.g., the standardized incidence for 1998 is calculated as:

$$\text{Standardized incidence, 1998} = \frac{\text{Number of new } n - \text{ grade revisions in the population in 1998}}{\text{Total population in Denmark in 1998}} * 100,000$$

Missing data: We expect to encounter some missing data. All missing data will be described.

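### No pooled incidence of third-or-later revisions is planned, and the display rule for small grades may prevent readers from summing it exactly

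*SAP*

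**What the plan says.** **Target group.** SAP section 1 (Background and rationale) says "We define three or more revisions on the same knee as being" multiply revised. The objective is to "investigate the incidence and prevalence of multiply revised knee arthroplasty patients". Protocol, Purpose, question 1 asks "how many multiple revisions procedures are performed (i.e. incidence").

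**Primary outcome.** PICOTS gives "Annual standardized prevalence and incidence of n-grade revisions following knee arthroplasty between 1998 and 2021 in Denmark".

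**Calculation.** SAP section 3 (Calculation of standardized incidence) takes the "number of new n-grade revisions performed as a proportion of the population in Denmark during a specific year" and adds "This is done for each level of revision, each year". No pooled level is defined.

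**Display.** Tables 2 and 3, Figure 2, Supplementary Figures 1-10 and Supplementary Tables 1-4 are all laid out by single grade. Grades are shown only above 10 occurrences. Table 3 adds that this is for all years; Table 2 and Figure 2 do not. The Figure 2 legend continues "for prevalence, >n-grade revisions are reported as well", and the supplementary figures repeat that limitation to prevalence. Figure 3 also keeps an open-ended group, but it too shows only prevalence, and it sums revisions over both knees.

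**The concern.** The SAP names one target group, grade 3 and above, and wants both its prevalence and its incidence. On the prevalence side the upper tail is kept in an open-ended group. On the incidence side grades that fail the threshold disappear, and no reason is given for the difference.

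Protocol question 1 counts procedures, so on the incidence side it needs grade 3 plus grade 4 plus grade 5 and so on. If upper grades are omitted, a reader who adds up the visible grades gets a lower bound of unknown tightness. Subtraction does not help either, because no output has a total-revisions column from which grades 1 and 2 could be removed. The quantity concerned is the burden in the very group the study was set up to describe.

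**Working it through.** **1. Where could a grade-3-or-more incidence appear?**
- Tables 2 and 3: annual counts by single grade, plus the highest grade performed that year. No pooled column and no total.
- Figure 2 and Supplementary Figures 1-10, incidence panels: single grades, no open-ended group.
- Supplementary Tables 1-4: rows for grades 1 to 5 and n, for 2021, by sex and age. The Total line in each block sums over age, not over grade.

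None gives the pooled figure.

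**2. What is given.** A knee becomes multiply revised at its third revision. Third-grade incidence is therefore the rate of newly multiply revised knees, and it is planned subject to the threshold.

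**3. How much could be hidden?** The documents give no counts by grade, so there is no figure to reproduce and this is an illustration only. Inputs:
- T = 1,048 revisions in 2020, and more than 20,000 over 20 years (Protocol, Size of the problem).
- q, the step from one grade to the next, is an assumption. The value 0.20 is suggested by the English registry study described in the Protocol under Re-revision. Those figures are cumulative risks over 13, 5 and 3 years, not shares within a calendar year, so q is varied from 0.10 to 0.35.

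Formulas: grade k = T(1 − q)q^(k−1); all grades 3 and above = Tq².

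*Rule applied per year, T = 1,048:*

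| q | Grade 3 | Grade 4 | Grade 5 | Grade ≥3 | Share hidden |
|---|---|---|---|---|---|
| 0.10 | 9.4 | 0.9 | 0.1 | 10.5 | 100% |
| 0.15 | 20.0 | 3.0 | 0.5 | 23.6 | 15% |
| 0.20 | 33.5 | 6.7 | 1.3 | 41.9 | 20% |
| 0.25 | 49.1 | 12.3 | 3.1 | 65.5 | 6% |
| 0.30 | 66.0 | 19.8 | 5.9 | 94.3 | 9% |
| 0.35 | 83.4 | 29.2 | 10.2 | 128.4 | 4% |

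At q = 0.20 only grade 3 is shown, so 41.9 − 33.5 = 8.4 of 41.9 are hidden (20%).

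*Rule applied to totals over the period, T = 20,000, q = 0.20:* grade 3 = 20,000 × 0.8 × 0.04 = 640, grade 4 = 128 and grade 5 = 26, all shown. Grade 6 and above = 20,000 × 0.2⁵ = 6.4. Grade ≥3 = 20,000 × 0.04 = 800. Hidden: 6.4/800 = 0.8%.

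*Rule requiring more than 10 in every year:* the SAP population has its primary procedure in 1998 or later, so few knees can reach a third revision in the first years. Grade 3 could then fail, and 100% would be hidden.

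*Rule applied per cell in Supplementary Tables 1-4, six equal sex-by-age cells (assumed):* grade 3 is 1.6 to 8.2 per cell for q = 0.10 to 0.25, so no grade-3-or-more incidence would be shown in those cells. At q = 0.30 and 0.35 it is 11.0 and 13.9, with 30% and 35% hidden.

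**4. The prevalence side.** The n in the open-ended group is not fixed, so that group need not itself mean three or more. If it begins where the displayed grades end, 3-or-more prevalence can still be summed. Incidence has no such remainder to add.

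**The case against.** A reader might infer that the incidence of multiply revised knees is reported nowhere. The documents do not support that: third-grade incidence is the rate of entry into the group, and it is planned in Tables 2-3, Figure 2 and, with its own row, Supplementary Tables 1-4, subject to the threshold. What is missing is the aggregate of procedures.

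A reader might also infer that the visible total will drift as grades cross 10 over time. That requires suppression year by year, which the SAP does not state. The rule speaks of which grades are shown. On either reading of Table 3's wording, a total over years or more than 10 in each year, a grade is in or out for the whole series.

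Finally, grade-specific reporting is the prespecified primary outcome, and the stated gap in knowledge is occurrence stratified by previous revisions. Pooled incidence also counts the same knee again at grades 4 and 5. Both points stand. They argue for placing the pooled series beside the primary outcome, labelled as procedures, and against making it the headline. They do not supply the number that question 1 asks for.

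**Conclusion.** The point holds in a limited form. No output gives the annual number or rate of grade-3-or-more procedures, and the threshold may prevent its exact recovery from the displayed grades. Entry into the group is covered by third-grade incidence, provided that grade is displayed.

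The size cannot be fixed from the documents. At an assumed 20% step the hidden share is 0.8% under a rule on period totals and 20% under a per-year rule. With steps of 15-35% the per-year share is 4-20%. It is 100% wherever grade 3 itself fails. These figures rest on a constant step between grades, an even sex-by-age split for the cell calculation, and a 2020 count that the protocol does not divide into major and minor revisions. Major-only outputs can only start from the same number or fewer. The omission and the unclear unit of the rule do not depend on these assumptions. This is an improvement available at almost no cost, not a flaw in the primary outcome.

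**What to change.** - Beside the grade-specific primary outcome, add a pooled 3-or-more series for incidence and prevalence to Figure 2, panels A-D, with a matching column in Tables 2 and 3.
- Label pooled incidence as procedures, and third-grade incidence as newly multiply revised knees.
- Extend the open-ended group to the incidence panels of Figure 2 and the supplementary figures, and define n, for example as the last grade displayed.
- State one unit for the more-than-10 rule (per year, per cell, or total over 1998-2021) and use it in every table and figure.

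The cost is one extra series per panel, one column in each of two tables and a few sentences in the SAP. All the data are already held, and pooling reduces the number of small cells that must be suppressed.

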## **SUPPLEMENTARY MATERIAL**

The anticipated (predefined) supplementary material of the manuscript is illustrated below.

**Supplementary file 1. Protocol**

[figure not shown]
[figure not shown]
**Supplementary file 2. This SAP**

**Supplementary Figure 1.** Standardized annual prevalence (panel A) and incidence rates (panel B) for major n-grade revisions for male sex

Only grades of revisions with occurrences >10 are shown; for prevalence, >n grade are reported as well.

[figure not shown]
[figure not shown]
**Supplementary Figure 2.** Standardized annual prevalence (panel A) and incidence rates (panel B) for major n-grade revisions for female sex.

Only grades of revisions with occurrences >10 are shown; for prevalence, >n grade are reported as well.

[figure not shown]
[figure not shown]

**Supplementary Figure 3: Standardized annual prevalence (panel A) and incidence rates (panel B) for major n-grade revisions for age group 18-49.**

[figure not shown]
[figure not shown]
Only grades of revisions with occurrences >10 are shown; for prevalence, >n grade are reported as well.

**Supplementary Figure 4:** Standardized annual prevalence (panel A) and incidence rates (panel B) for major n-grade revisions for age group 50-69.

[figure not shown]
[figure not shown]
Only grades of revisions with occurrences >10 are shown; for prevalence, >n grade are reported as well.

**Supplementary Figure 5.** Standardized annual prevalence (panel A) and incidence rates (panel B) for major n-grade revisions for age group 70-99.

[figure not shown]
[figure not shown]
Only grades of revisions with occurrences >10 are shown; for prevalence, >n grade are reported as well.

**Supplementary Figure 6:** Standardized annual prevalence (panel A) and incidence rates (panel B) for all n-grade revisions (including major and minor revisions) for male sex.

[figure not shown]
[figure not shown]
Only grades of revisions with occurrences >10 are shown; for prevalence, >n grade are reported as well.

**Supplementary Figure 7:** Standardized annual prevalence (panel A) and incidence rates (panel B) for all n-grade revisions (including major and minor revisions) for female sex.

[figure not shown]
[figure not shown]
Only grades of revisions with occurrences >10 are shown; for prevalence, >n grade are reported as well.

**Supplementary Figure 8:** Standardized annual prevalence (panel A) and incidence rates (panel B) for all n-grade revisions (including major and minor revisions) for age group 18-49.

[figure not shown]
[figure not shown]
Only grades of revisions with occurrences >10 are shown; for prevalence, >n grade are reported as well.

**Supplementary Figure 9:** Standardized annual prevalence (panel A) and incidence rates (panel B) for all n-grade revisions (including major and minor revisions) for age group 50-69.

Only grades of revisions with occurrences >10 are shown; for prevalence, >n grade are reported as well.

**Supplementary Figure 10:** Standardized annual prevalence (panel A) and incidence rates (panel B) for all n-grade revisions (including major and minor revisions) for age group 70-99.

Only grades of revisions with occurrences >10 are shown; for prevalence, >n grade are reported as well.

**Supplementary table 1:** Age-stratified prevalence and incidence of major n-grade revisions for females, Denmark 2021.

Grade of revision	Age group	No. of procedures	No. of persons in Denmark on the 1 st of January in 2021	Prevalence per 100.000	Incidence per 100.000
1 st	Total				
	18-49				
	50-69				
	70-99				
2 nd	Total				
	18-49				
	50-69				
	70-99				
3 rd	Total				
	18-49				
	50-69				
	70-99				
4 th	Total				
	18-49				
	50-69				
	70-99				
5 th	Total				
	18-49				
	50-69				
	70-99				
n-grade	Total				
	18-49				
	50-69				
	70-99				

Only grades of revisions with occurrences >10 are shown.

**Supplementary table 2:** Age-stratified prevalence and incidence of major n-grade revisions for males, Denmark 2021.

Grade of revision	Age group	No. of procedures	No. of persons in Denmark on the 1 st of January in 2021	Prevalence per 100.000	Incidence per 100.000
1 st	Total				
	18-49				
	50-69				
	70-99				
2 nd	Total				
	18-49				
	50-69				
	70-99				
3 rd	Total				
	18-49				
	50-69				
	70-99				
4 th	Total				
	18-49				
	50-69				
	70-99				
5 th	Total				
	18-49				
	50-69				
	70-99				
n-grade	Total				
	18-49				
	50-69				
	70-99				

Only grades of revisions with occurrences >10 are shown.

**Supplementary table 3:** Age-stratified prevalence and incidence of all n-grade revisions (including major and minor revisions) for females, Denmark 2021

Grade of revision	Age group	No. of procedures	No. of persons in Denmark on the 1 st of January in 2021	Prevalence per 100.000	Incidence per 100.000
1 st	Total				
	18-49				
	50-69				
	70-99				
2 nd	Total				
	18-49				
	50-69				
	70-99				
3 rd	Total				
	18-49				
	50-69				
	70-99				
4 th	Total				
	18-49				
	50-69				
	70-99				
5 th	Total				
	18-49				
	50-69				
	70-99				
n-grade	Total				
	18-49				
	50-69				
	70-99				

Only grades of revisions with occurrences >10 are shown.

**Supplementary table 4:** Age-stratified prevalence and incidence of all n-grade revisions (including major and minor revisions) for males, Denmark 2021

Grade of revision	Age group	No. of procedures	No. of persons in Denmark on the 1 st of January in 2021	Prevalence per 100.000	Incidence per 100.000
1 st	Total				
	18-49				
	50-69				
	70-99				
2 nd	Total				
	18-49				
	50-69				
	70-99				
3 rd	Total				
	18-49				
	50-69				
	70-99				
4 th	Total				
	18-49				
	50-69				
	70-99				
5 th	Total				
	18-49				
	50-69				
	70-99				
n-grade	Total				
	18-49				
	50-69				
	70-99				

Only grades of revisions with occurrences >10 are shown.

